## 5.1.5 Randomisation & Allocation

A third party provider "Sealed Envelope", which provides its services free to PhD students, will be used to provide a web based randomisation service with a telephone as back up. Once eligibility criteria have been confirmed, consent is obtained and stratification variables determined through clinical/radiographic examination, the

Non-CTIMP Version number: V 2.0

Version date: 11/06/2019

randomisation can be performed. The allocation of participants into either control arm or intervention arm will be concealed to the operator until all outcome measures have been collected.

To ensure the test and control groups are matched and chance imbalances are avoided in important stratification variables, a computer based "minimisation" algorithm will be used. The variables chosen are:

- Age (18 30 / 31 50 / > 51)
- Gender
- Ethnicity
- Size of apical lesion (1 5 mm / > 6 mm)

The procedures for randomisation will be fully documented and piloted prior to the start of the trial.

#### 5.2 Data Collection

#### i) Profile of inflammatory mediators

A recent literature review conducted by our group has revealed the most common approach for sampling and analysing the concentrations of periradicular inflammatory mediators during NSRCT is using paper points and proteomic molecular analysis techniques respectively ([name] *et al.* 2019). Through in vitro experimentation, our group has optimised the sampling and elution procedure so that the maximum amount of PTF is absorbed onto the paper point, and the maximum amount of cytokine is recovered during elution. Briefly, this will be passively achieved by placing an endodontic absorbent paper point (Panadent, Kent, UK) 2 mm past the apex for 60 seconds in a dry canal. The baseline sample will be taken on the first treatment visit prior to any intervention and then the second taken from the same tooth on the second treatment visit approximately 14 days later. The volume of extracted PTF will be determined using a wetted length to volume standard curve (Shimauchi et al., 1996). Once sampled, the PTF will be immersed in elution buffer and processed on clinic by vortexing for 60 seconds and then stored in a – 80°C freezer at the Birmingham Dental School Research Laboratory (HTA licence – 12236). When ready to analyse, samples will be thawed at room temperature and the supernatant extracted and will undergo proteomic multiplex analysis to evaluate the concentration of a broad spectrum of inflammatory mediators.

ii) Clinical information

| History               | Presenting complaint, pain history, pain score                      |  |  |  |
|-----------------------|---|--|--|--|
| Clinical findings     | Visual Condition of the hard tissue, presence of swelling and sinus |  |  |  |
|                       | Symptoms Tenderness to percussion, palpation, mastication           |  |  |  |
|                       | Periodontal Periodontal pocket depth, mobility score                |  |  |  |
| Special tests         | Vitality of tooth   |  |  |  |
| Radiographic findings | Presence and size of radiographic lesion                            |  |  |  |

The following clinical information will be collected:

This data will be collected on a case report form (CRF) at the pre-operative appointment and the 12 month review by the chief or principle investigator.

#### 5.3 Analysis of Outcome Measures

Appropriate statistical analysis will be conducted to identify if there is any significant difference in the concentration change of specific cytokines in both test and control group. Statistical analysis will also be conducted to identify correlations between clinical signs of apical periodontitis and individual mediator concentration.

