#### ii) Secondary Outcomes

- Determine profile of key inflammatory mediators in the presence of active disease and following treatment

To establish changes in the concentration of periradicular inflammatory mediators, periradicular tissue fluid (PTF) will be retrieved from the apical tissues associated with teeth at the start of and following NSRCT. This will be achieved by placing a paper point 2 mm beyond the end of the root canal for 60 seconds in a dry canal. The baseline sample will be taken on the first treatment visit prior to any intervention and then the second taken from the same tooth on the second treatment visit approximately 14 days later. The volume of extracted PTF will be determined using a wetted length to volume standard curve (Shimauchi et al., 1996). Once sampled, the PTF will be immersed in elution buffer and processed on clinic by vortexing for 60 seconds and then stored in a  $- 80^{\circ}$ C freezer at the Birmingham Dental School Research Lab. When ready to analyse, samples will be thawed at room temperature and the supernatant will undergo proteomic multiplex analysis to evaluate the concentration of a broad spectrum of inflammatory mediators, which will be represented in pg/ml. Through in vitro investigation our research group has optimised the sampling and elution procedure so that the maximum amount of PTF is absorbed onto the paper point, and the maximum amounts of analytes are recovered during elution.

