## Study design and methods of data collection and data analysis

#### 5.1 Study Design

This pilot study has been designed as a parallel group randomised clinical trial design to compare the outcomes of standard care (NSRCT with a conventional irrigation technique) against the experimental intervention (NSRCT with an irrigation protocol to optimise release of soluble dEMCs). To generate preliminary data a total sample size of up to 40 participants, with up to 20 per group, will be required.

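### Section 5.3 sets the mediator comparison as concentration change without committing to adjust for the baseline sample; adjusting would cut variance by 15% to 40% for assumed correlations of 0.7 to 0.2

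*Protocol*

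**What the plan says.** The mediator profile is the secondary outcome (Protocol, Outcome, ii) Secondary Outcomes). One paper-point sample is taken at the first visit before any intervention, and a second from the same tooth about 14 days later. The multiplex assay is to "evaluate the concentration of a broad spectrum of inflammatory mediators". The outcome heading speaks of "Determine profile of key inflammatory mediators in the presence of active disease and following treatment", but no mediator is named and the panel size is not given.

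Section 5.3 is the only analysis section. It opens "Appropriate statistical analysis will be conducted" and sets the aim to "identify if there is any significant difference in the concentration change of specific cytokines in both test and control group". It then adds: "Statistical analysis will also be conducted to identify correlations between clinical signs of apical periodontitis and individual mediator concentration". It mentions no covariate, scale or significance level.

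Section 5.1.5 makes the size of the apical lesion a minimisation factor. On numbers, section 5.1 says: "To generate preliminary data a total sample size of up to 40 participants, with up to 20 per group, will be required". Section 5.1.1 gives no power calculation and rests the size on earlier mediator studies.

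**The concern.** The method is left open, but the quantity to be compared is written down as change. Subtracting one noisy baseline value from one noisy follow-up value adds the baseline noise to the outcome. Unless the analysis also adjusts for baseline, precision is lost, and with at most 20 patients per arm there is little to spare. The data needed for the better analysis are already collected.

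The sentence in 5.3 also refers to change in both groups. Taken alone, it could be read as a before/after test in each arm, which would not compare the treatments.

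The panel is broad and no mediator is ranked first, so some nominally significant results may be chance. The protocol's Theoretical framework says that the mediator work could guide which cytokines to target in later research. That is where imprecise or chance results would do harm.

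**Working it through.** The protocol gives no power, alpha or calculated sample size for the mediators, so there is no figure to reproduce.

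**Inputs**
- Patients per arm: 20, the maximum in section 5.1.
- Two-sided alpha 0.05 per mediator and 80% power: assumed.
- Baseline/follow-up correlation r: not given; assumed 0.2 to 0.7.
- Equal variance s² at both visits: assumed.
- Number of mediators: not given; 10 to 30 assumed.

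**1. Precision**

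Per-patient variance of an unadjusted change score: 2(1 − r)s². Residual variance after adjusting for baseline: (1 − r²)s². The ratio is (1 − r²) / [2(1 − r)] = (1 + r)/2.

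| r | variance ratio (1+r)/2 | ratio with a degrees-of-freedom penalty, ×(1 + 1/36) |
|---|---|---|
| 0.2 | 0.60 | 0.617 |
| 0.3 | 0.65 | 0.668 |
| 0.5 | 0.75 | 0.771 |
| 0.7 | 0.85 | 0.874 |
| 0.9 | 0.95 | 0.976 |

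In patients, an unadjusted change score needs 2/(1 + r) times as many: 1/0.60 = 1.67 times at r = 0.2 and 1/0.85 = 1.18 times at r = 0.7. The ratio is below 1 for every r below 1. With the penalty it reaches 1 only at r of about 0.95, from 2/(1 + 1/36) − 1 = 0.946.

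Below r = 0.5 the factor 2(1 − r) exceeds 1, so an unadjusted change score is then noisier than comparing second-visit values with no use of baseline.

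**2. Detectable effect**

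A two-sample t-test with 20 per arm, alpha 0.05 and 80% power detects 0.909 SD. Multiply by √(2(1 − r)) for change and √(1 − r²) for the adjusted analysis:
- r = 0.3: change 0.909 × 1.183 = 1.08 SD; adjusted 0.909 × 0.954 = 0.87 SD.
- r = 0.5: change 0.909 × 1.000 = 0.91 SD; adjusted 0.909 × 0.866 = 0.79 SD.

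**3. Power for an assumed true difference of 0.8 SD, 20 per arm (normal approximation)**
- r = 0.3: 57% for change, 76% adjusted.
- r = 0.5: 72% for change, 83% adjusted.
- r = 0.7: 90% for change, 94% adjusted.

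**4. Log scale**

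In simulated log-normal data at r = 0.5 with a 0.8 SD effect on the log scale, power for raw change / log change / log-scale ANCOVA was:
- log-SD 0.5: 69% / 69% / 81%
- log-SD 1: 53% / 70% / 81%
- log-SD 1.5: 35% / 70% / 81%

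The gain from logs therefore depends on skew, which the protocol does not report. The gain from baseline adjustment on the log scale is there at each log-SD.

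**5. Chance findings**

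With k independent tests at 5%, the chance of at least one false positive is 1 − 0.95^k. Simulation (20 per arm) gives the values for correlated mediators.

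| mediators | independent | correlation 0.3 | 0.5 | 0.7 |
|---|---|---|---|---|
| 10 | 40% | 36% | 29% | 22% |
| 20 | 64% | 55% | 43% | 28% |
| 30 | 79% | 67% | 51% | 35% |

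Reaching 95% takes about 59 independent tests (1 − 0.95^59 = 0.952). The correlations with clinical signs would add further tests, of a number not stated.

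**The case against.** The strongest reply is that change does not rule out the better analysis. ANCOVA of change with baseline as covariate gives the same treatment estimate and standard error as ANCOVA of the second-visit value with the same covariate. The protocol never specifies an unadjusted test, and model, scale and covariates are commonly left to an analysis plan, which is not shown. This stands in large part: the loss calculated here would arise only if an analysis plan took the wording of 5.3 at face value. But nothing in the protocol commits to the adjustment, and the one quantity it names is change.

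Some stronger readings are tempting, and the protocol does not support them:
- *The baseline sample goes unused.* A change from baseline uses it; the point is that it may be used inefficiently. Lesion size is used in the minimisation.
- *Regression to the mean biases the comparison.* Under randomisation it acts on both arms alike in expectation. What remains is precision and chance baseline imbalance.
- *Only before/after tests within arms are planned.* Background, Research question/aims and Objectives all set the intervention against conventional treatment. The phrase in 5.3 is loose, but the intended contrast is between arms.
- *The whole panel will be tested, so a false finding is near-certain.* The assay is broad, but 5.3 speaks of specific cytokines and does not commit to testing all of them. For 10 to 30 mediators the risk is 22% to 79%, depending on number and correlation.
- *The lack of a multiplicity rule is an error.* An analysis plan may hold one. False-discovery control would also limit the expected share of false findings rather than prevent them, and would cost power at this size.

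**Conclusion.** The point holds as a recommended improvement in method. A baseline-adjusted between-arm comparison is more precise than an unadjusted change score: its variance is 0.60 to 0.85 as large for r of 0.2 to 0.7, a cut of 40% to 15%. The size rests on an assumed r and on equal variances at the two visits. Given equal variances, the direction does not depend on r, except at very high values where the lost degrees of freedom cancel the gain. A benefit from the log scale is conditional on skew. The risk of chance findings supports naming lead mediators, but that is advice and not a fault in the protocol. The primary outcome is unaffected; what is at stake is how well the mediator results of a pilot can be interpreted and used.

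**What to change.** In section 5.3, state that each mediator's second-visit concentration (or its change from the first visit) is compared between arms by ANCOVA. The covariates are baseline concentration and lesion size, the latter because it is a minimisation factor. Use the log scale if the data are skewed. State also that before/after tests within an arm are not used as evidence of a treatment effect.

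Optional: name one or two lead mediators before unblinding, and label the remaining mediators and the correlations with clinical signs as exploratory.

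Cost: a few lines of text and one or two degrees of freedom out of about 38. No extra samples or visits are needed. If logs are used, the analysis must also say how undetectable concentrations are handled.

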## Study setting

The whole study (i.e. recruitment, intervention, data collection and data analysis) will be conducted at the Birmingham Dental Hospital. This site receives referrals from general dental practitioners regarding patients requiring management of apical periodontitis and will therefore be ideal for recruiting patients into the study. Potential participants will be accessed through restorative consultation and acute dental clinics which are held on a daily basis. Birmingham Dental Hospital and School have its own HTA licence (No: 12313) for research and is experienced in handling human tissue samples (relevant material). Furthermore, there is an onsite laboratory which contains the necessary equipment to store, monitor and analyse the biological samples (periradicular tissue fluid) retrieved from patients.

#### Participant recruitment

## Eligibility Criteria

#### 5.3.1 Inclusion criteria

- Patients diagnosed with apical periodontitis
- Single rooted permanent teeth
- Medically fit
- Adult patients (≥ 18)
- Voluntarily consent to partake in the study

#### 5.3.2 Exclusion criteria

- Teeth in sextants with active periodontal disease (i.e. pocketing of  $\leq 5$  mm)
- Tooth unable to retain a rubber dam
- Teeth that have had previous endodontic treatment
- Root apex in close proximity to the maxillary sinus
- Patients who have had antimicrobial therapy within 3 months prior to the screening clinic
- Pregnant or breastfeeding women
- Do not have capacity to consent
- Patients that have systemic condition that would reduce immune function

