## **Population Studied**

Inclusion Criteria:

- Patients diagnosed with apical periodontitis
- Single rooted permanent teeth
- Medically fit
- Adult patients ( $\geq$  18)
- Voluntarily consent to partake in the study

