#### Exclusion Criteria:

- Teeth in sextants with active periodontal disease (i.e. pocketing of  $\leq$  5 mm)
- Tooth unable to retain a rubber dam
- Teeth that have had previous endodontic treatment
- Root apex in close proximity to the maxillary sinus

- Patients who have had antimicrobial therapy within 3 months prior to the screening clinic
- Pregnant or breastfeeding women
- Do not have capacity to consent
- Patients that have systemic condition that would reduce immune function

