#### 5.1.1 Number of Participant

As the proposed analysis has not been previously reported, a power calculation to determine a statistically appropriate sample size cannot be performed. The proposed sample size (up to 40) is therefore based on previous studies which have analysed the changes in concentrations of various periradicular inflammatory mediators during NSRCT.

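### The periodontal exclusion criterion has its inequality reversed: as written it excludes shallow pocketing and lets deep pocketing through.

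*Protocol*

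**What the plan says.** The protocol states the criterion twice. Section 5.3.2 (Exclusion criteria) reads "Teeth in sextants with active periodontal disease (i.e. pocketing of $\leq 5$ mm"), and the Exclusion Criteria list in the Study summary reads "Teeth in sextants with active periodontal disease (i.e. pocketing of $\leq$ 5 mm"). Wording and direction are the same in both. The abbreviation before the figure presents it as the definition of active disease, not as an example of it. No other section gives a different depth, a lower bound or another definition.

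The rule is meant to be applied. The Patient Pathway has a research clinician confirm eligibility against the listed criteria at the screening clinic. The clinical-information table in section 5.2 (Data Collection) includes "Periodontal pocket depth, mobility score" among the findings entered on the case report form before treatment and at 12 months.

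**The concern.** The label and its numerical definition point in opposite directions. The criterion is there to keep periodontally diseased sextants out of the trial, yet the depth rule attached to it removes sextants with shallow or normal pocketing and retains those with deep pocketing.

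There are two ways to apply the text, and neither is satisfactory:

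- **Follow the number.** The trial turns away the patients it presumably wants, and this criterion admits those it means to exclude. Periodontal pain or swelling could then be counted in the primary outcome (section Outcome), which rests on pain, swelling, sinus tract, tenderness and lesion size. Effects on lesion size and on the mediator samples are plausible, but the protocol does not demonstrate them.
- **Follow the label.** Clinicians enrol sensibly, but each enrolled patient with pocketing of 5 mm or less contradicts the written rule, and the recorded depth documents it. Under Regulatory Review & Compliance, deviations are among the triggers for an on-site monitoring visit.

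The minimisation variables in section 5.1.5 are age, gender, ethnicity and lesion size. Periodontal status is not among them, so any diseased teeth that entered would be balanced between arms only by chance.

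**Working it through.** No sample-size or power figure is involved; section 5.1.1 states that "a power calculation to determine a statistically appropriate sample size cannot be performed". The check is a reading of the rule.

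**1. Apply the rule literally.** Exclude if depth ≤ 5 mm; do not exclude if depth > 5 mm. Taking depth as the deepest pocket in the sextant:

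| Deepest pocket (mm) | Meets the written definition? | Result under this criterion |
|---|---|---|
| 1, 2, 3, 4, 5 | Yes | Excluded |
| 6, 7, 8 | No | Not excluded |

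The excluded set is the shallow end of the scale, contrary to the label. All sextants at or below 5 mm fail and all above 5 mm pass. That is a property of the rule, not an estimate of enrolment error.

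**2. Try the other reading of depth.** The text does not say whether the deepest site or any site counts. If any site at or below 5 mm triggers exclusion, nearly every sextant is excluded. This reading does not rescue the criterion either.

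**3. Consider whether the sign was misread from the PDF.**

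| Criterion | Study summary | Main text | Direction |
|---|---|---|---|
| Age | "Adult patients ( $\geq$ 18") | "Adult patients (≥ 18") | As expected, both times |
| Pocketing | "Teeth in sextants with active periodontal disease (i.e. pocketing of $\leq$ 5 mm") | "Teeth in sextants with active periodontal disease (i.e. pocketing of $\leq 5$ mm") | Against its label, both times |

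The age sign comes through correctly in both inclusion lists, and the pocketing sign is the same in both exclusion lists. Two identical misreadings beside two correct readings are improbable, though only the PDF can exclude this entirely.

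**4. Size of one error.** Section 5.1 allows up to 20 participants per group. One misclassified outcome changes that arm's success rate by 1/20 = 0.05, or 5 percentage points. This holds for a misclassification from any cause; it shows how little slack a trial of this size has and does not predict how many errors would occur.

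**The case against.** The strongest reply is that nobody would apply the rule backwards. The criterion leads with a clinical description, and the figure is a gloss in brackets. Eligibility is judged by a research clinician, and the person taking consent must be trained and know the protocol. To enrol the opposite population, that clinician would have to call shallow pockets diseased and deep pockets healthy. This stands as a limit on the consequence: ambiguous eligibility and paper non-compliance are more likely than wholesale wrong enrolment. It does not make the text right, because a clinician who follows the label departs from the stated definition.

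The route to biased outcomes is also partly conjecture. Apical lesions are to be measured on three-dimensional scans (Assessment and management of risk), fluid is drawn through the canal from beyond the apex (section 5.2), and the pocketing may be at a neighbouring tooth in the sextant. The protocol does not link such pocketing to a misclassified outcome. Eligibility errors would also precede randomisation, so they could fall in either arm and would be expected to add noise or limit generalisability rather than favour one arm systematically. These points stand, and the lesion-size and mediator routes should be taken as plausible only.

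Finally, the screening form is not among the documents, so whether it repeats the error is unknown.

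**Conclusion.** The concern holds. An operative eligibility threshold contradicts its own label in both places where it appears, and nothing elsewhere in the protocol corrects it. The inversion of the written rule is total; its effect on actual enrolment cannot be quantified from the protocol and is probably tempered by clinical judgement. The conclusion assumes that the sign was read correctly from the PDF, which the correctly read age criterion supports. It does not depend on whether the deepest site or any site is meant, since the rule fails either way. It makes no claim about which pocket depth should define active disease. It should be corrected because it governs who enters the trial, and compliance with it will be judged against recorded measurements.

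**What to change.** Reconcile the sign with the label in section 5.3.2 and in the Study summary, so that the numerical rule excludes the sextants the label describes. Check the screening form and correct it if it carries the same sign. In the same amendment the sponsor should:

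- confirm the threshold;
- state whether exactly 5 mm is in or out, since turning the sign does not by itself settle this;
- state whether depth means the deepest site or any site in the sextant.

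If patients have already been enrolled, compare their recorded pre-operative pocket depths with the clarified rule and document the result.

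The cost is a one-character change in two places, a short clarifying phrase and any matching change to the screening form, taken through the Amendments procedure. Sample size, visits and analysis are unaffected.
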